- b. Noncardiac MAPE including sepsis, renal failure, unexpected intensive care unit (ICU) admission and respiratory disorders.
- c. All-cause mortality

3. To examine whether (combinations of) perioperatively measured biomarkers are associated with 6-month MACE and all-cause mortality in patients undergoing elective noncardiac surgery.
4. To assess the added value of the perioperatively measured biomarkers on top of the currently used Revised Cardiac Risk Index (RCRI) to predict MACE after noncardiac surgery.

Study design

This prospective observational cohort study includes patients, aged 60 years and older, undergoing elective intermediate or high risk noncardiac surgery under spinal or general anesthesia with an expected postoperative hospital admittance of at least 24h. All patients are required to visit the preanesthesia outpatient clinic for preoperative consultation. In addition to care as usual, extra blood samples will be taken preoperatively and postoperatively up to three days after surgery to determine the following biomarkers: high sensitive troponin, brain natriuretic protein, C-reactive protein, creatinine and hemoglobin. At postoperative day 2, extra to routine care noninvasive imaging (i.e. electrocardiography and transthoracic echography) will be performed. Preoperatively measured biomarkers are considered baseline measurements. Biomarker values will be blinded from treating physicians in case this particular biomarker was not measured in routine care. In-hospital MAPE will be monitored including cardiac events, respiratory failure, pulmonary embolism, sepsis, renal failure and mortality. In addition, patients will be asked to fill out the WHODAS 2.0 questionnaire preoperatively and 6 months after their surgery to assess disability. Their general practitioners (GPs) will be approached to determine whether MACE and/or mortality have occurred during the 6 months follow up after surgery.

Study population

Patients aged >60 years undergoing elective intermediate (e.g. hip replacement) or high risk (e.g. liver resection) noncardiac surgery under general or spinal anesthesia with a postoperative hospital stay of at least 24 hours are eligible for participation in this study. We aim to include 500 patients in this study. Approximately 1,200 patients undergo elective major noncardiac surgery each year in the UMC Utrecht. Taking into account nonparticipation and potential lower inclusion rates at the

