4.4 Sample size calculation

For this study, we aim to include 500 patients at the UMCU in this study. A similar study will be conducted at the University Health Network Toronto (UHNT), Toronto, Canada and they will include 500 patients with the same in- and exclusion criteria. After including all patients in both centers, we will combine the data resulting in a total study population of 1,000 patients. In a previous conducted pilot study by the UHNT (registered at ClinicalTrial.gov: NCT02146560), 300 patients undergoing major elective noncardiac surgery were included and disability was assessed by the WHODAS 2.0 after 6 months. The incidence of troponin elevation in this pilot was 14.1%. We do however expect an incidence of 11.0% as patients included in the pilot were mainly vascular patients, who are more

prone to have postoperative troponin elevations⁴. The mean WHODAS 2.0 in patients with an elevation in troponin was 29% compared to 15% in patients without troponin elevation. Based on these results, and using a level of significance of 0.05 and a power of 0.8 we expect 104 patients with troponin elevation. As the ratio between troponin elevation and no troponin elevation is $0.89/0.11 = 8$, we need to include 832 patients. We expect a dropout of 20% (based on the number of patients who did not fill out the WHODAS 2.0 after 6 months in the pilot study), leading to a final sample size of approximately 1,000 patients.

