7. STATISTICAL ANALYSIS

7.1 Data description

Baseline characteristics will be presented using percentages for categorical covariates, means with standard deviations and/or medians with interquartile ranges for continuous variables. Comparison between baseline characteristics will be done using the chi-square test for categorical variables and Student's t-test or Mann Whitney-U test for continuous variables as appropriate. Based on a pilot study conducted at UHNT, we assume a patient dropout of 20% at 6 months follow up (see Sample size calculation). Baseline characteristics of patients who did and did not respond at 6 months follow up will be compared to examine whether selective dropout occurred. Multiple imputation will be performed in case of any missing data. Throughout the analyses, a *p*-value of 0.05 is considered statistically significant.

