- The added prognostic value of each of the biomarkers (or combinations of biomarkers) will be tested to predict MACE, both in-hospital and at 6-months. The biomarkers will be analyzed as continuous variables and using predefined clinical thresholds to define whether that particular biomarker is elevated. Multivariable logistic regression analyses will be performed using the predictors of the RCRI (i.e. high risk surgery, history of cerebrovascular disease, history of myocardial infarction, congestive heart failure, elevated creatinine and insulin dependent diabetes) as predictors together with the addition of elevation in biomarkers. Discrimination and calibration of the prediction models will be assessed using the c-statistic, Hosmer-Lemeshow test. The net reclassification index (NRI) and the Integrated Discrimination Index (IDI) will be calculated to quantify how well the updated RCRI reclassifies patients as compared to the traditional RCRI.

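### The Hosmer-Lemeshow test is the only calibration check planned for the RCRI-plus-biomarker models; it gives no size or direction of miscalibration and has low power against a wrongly shaped biomarker effect

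*Combined protocol and SAP*

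**What the plan says.** Secondary objective 4 (section 2.2) asks what the biomarkers add to the RCRI for predicting MACE. The method is the last bullet of section 7.3:

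- **Model.** "Multivariable logistic regression analyses will be performed using the predictors of the RCRI", with biomarkers added. The coefficients are estimated in the study data; no published RCRI risks are carried over.
- **Form of the biomarkers.** "The biomarkers will be analyzed as continuous variables and using predefined clinical thresholds". No transformation or linearity check is mentioned.
- **Performance.** "Discrimination and calibration of the prediction models will be assessed using the c-statistic, Hosmer-Lemeshow test".
- **Reclassification.** "The net reclassification index (NRI) and the Integrated Discrimination Index (IDI) will be calculated to quantify how well the updated RCRI reclassifies patients".

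Section 7.1 sets the significance level: "Throughout the analyses, a *p*-value of 0.05 is considered statistically significant". It gives no separate rule for a goodness-of-fit test.

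On size, the Summary says "We aim to include 500 patients in this study" for Utrecht. Section 4.4 adds 500 patients from Toronto: "we will combine the data resulting in a total study population of 1,000 patients".

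**The concern.** Good calibration means that predicted and observed risks agree. Showing it requires an estimate of the disagreement and its uncertainty. The Hosmer-Lemeshow test returns only a p-value. A non-significant result may mean that the model fits, or that there were too few events to show that it does not.

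Two features of section 7.3 sharpen this. The model is judged in the data used to fit it, so the forms of miscalibration that matter most in new patients cannot appear. And continuous biomarkers enter with no check of linearity, so a wrong functional form is a realistic fault for the test to miss.

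At stake is what can be said about the updated RCRI. Its predicted risks could be reported with no usable calibration evidence. NRI and IDI are computed from the same predicted risks, so an undetected misfit enters them too.

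**Working it through.** The plan gives no figure for calibration, for the power of this test or for MACE events, so there is no planned figure to reproduce.

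**1. What assesses calibration.** The c-statistic measures discrimination; NRI and IDI measure reclassification and discrimination. Only the Hosmer-Lemeshow test addresses calibration. No calibration plot, intercept, slope, observed/expected ratio or validation step appears anywhere in the document.

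**2. What a same-data check can show.** Maximum likelihood for a logistic model solves Σ(y − p̂) = 0 and Σ x_j(y − p̂) = 0 for every predictor. Hence Σ LP(y − p̂) = 0, where LP is the fitted linear predictor. Recalibrating in the same data therefore returns intercept 0 and slope 1 exactly.

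A simulation shows the consequence. It used six RCRI items plus three biomarkers, a correct functional form, N = 500-1,000, assumed MACE rates of 3.6-10% and 300 trials per setting:

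| Quantity | Result |
|---|---|
| Slope in the fitting data, mean | 1.000 |
| Slope in new patients, median by setting | 0.43-0.81 |
| Hosmer-Lemeshow p < 0.05 | 4-7% of trials |
| Hosmer-Lemeshow p > 0.05 among fits with new-patient slope below 0.8 | 94-97% |

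The test rejects at about its nominal rate even when the model is badly overfitted.

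**3. Assumed MACE rate.** The Introduction reports MAPE in 19% of patients, 19% of it cardiovascular. If the second figure is a share of MAPE, 0.19 × 0.19 = 3.6%. Alternatively, 11% troponin elevation (section 4.4) with one third being infarction gives 0.11/3 = 3.7%. At 3.6%, 500 patients yield 18 events and 1,000 yield 36. Rates up to 10% were also used. Section 7.3 elsewhere counts PMI and NITE within MACE, which would raise the rate to about 11-15%.

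**4. Power against a wrongly linear biomarker.** The statistic is Σ (O − E)² / [E(1 − E/n)] over ten risk groups, referred to chi-square with 8 degrees of freedom at 0.05. The first shape used six binary RCRI items (odds ratio 2.2 each) and one standard-normal marker with log-odds 0.5x + 0.3(x² − 1), entered as linear. The second was a monotone hinge: flat, then rising.

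| True shape | Detection, N = 500-1,000, MACE 3.6-10% |
|---|---|
| U-shaped | about 18-27% |
| Monotone hinge | about 9-12% |

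Repeats agreed to within a few points. The U-shape gave 15-20% at N = 500 and 22-28% at N = 1,000 over MACE rates of 3.6-15%. The hinge and a convex monotone shape gave 4-12% over 5-15%. Under a correct model the test rejected in 4-5%.

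**5. Dependence on strength.** In a model with the marker alone and log-odds 0.8x + qx², at MACE 3.6-10%, the test missed 72-85% with q = 0.2 (detected 15-28%) and 13-54% with q = 0.4 (detected 46-87%). Strong curvature in a marker-only model is thus often found.

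**6. What an interval would show.** Approximate 95% limits for observed/expected around 1 are exp(±1.96 √[(1 − p)/events]):

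- N = 500, 3.6%: √(0.964/18) = 0.231, giving 0.64-1.57.
- N = 1,000, 3.6%: √(0.964/36) = 0.164, giving 0.73-1.38.
- N = 1,000, 10%: √(0.90/100) = 0.095, giving 0.83-1.20.

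These limits show how much is known; a p-value does not.

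**The case against.** **No pass rule is written.** The documents never say that a non-significant result means adequate calibration; section 7.1 sets only a general level. This stands. A reader might infer the rule, but it is not plan text. What remains is that no other calibration evidence is planned.

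**No general miss rate can be given.** A reader might want one percentage for how often the test fails. The documents supply no MACE rate and no size of relevant miscalibration. Over wider assumptions the miss rate runs from about 0% to 98%. Both extremes come from fixed predictions with a wrong slope or intercept, which section 7.3 does not plan because it refits the model. Only figures tied to a stated same-data misfit are usable.

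**The size of the error in predicted risk is not established.** A reader might infer that risks at low marker values would be wrong by a factor of two to three. That follows from the U-shape, whose minimum lies at x = −0.5/0.6 = −0.83, so that risk rises again in about 20% of patients as the marker falls. Nothing in the documents supports such a reversal. At 5% MACE, predicted versus true risk in the lowest marker decile was 1.1% vs 3.5% (ratio 3.2) for the U-shape, 1.6% vs 3.1% (1.9) for the hinge and 2.2% vs 3.1% (1.4) for the convex shape. The low power survives the change of shape; the size of the error does not.

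**A direct test of curvature is not always much better.** At N = 1,000 a one-degree-of-freedom quadratic test detected the U-shape in 75-99% of trials, but that is the term that generated the data. It found the hinge in 36-74% and the convex shape in 27-42%. This stands, and it favours modelling non-linearity from the start over testing for it.

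**Threshold models are less exposed.** A single marker entered as yes/no cannot be wrongly linear. This stands and limits the power argument to the continuous-biomarker models.

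**A calibration curve drawn in the fitting data has the same weakness.** Correct: it would hide overfitting as the test does. The fix below takes this into account.

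**Conclusion.** The point holds in limited form. The Hosmer-Lemeshow test is the only calibration assessment in section 7.3, and it reports neither size nor direction. That part needs no assumption. Because the models are refitted and checked in the same data, it also cannot reveal overfitting.

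Against a continuous biomarker wrongly entered as linear, detection is roughly 9-27% at N = 500-1,000. This rests on assumed MACE rates of 3.6-10%, assumed RCRI prevalences and effects, and the two shapes simulated. Gentler shapes are found less often and strong curvature more often.

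Only secondary objective 4 is affected. The primary analysis of disability is untouched, and nothing here shows that the updated RCRI will in fact be miscalibrated. It is an inexpensive improvement to the analysis plan.

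**What to change.** In section 7.3:

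1. Replace the Hosmer-Lemeshow test with a smoothed calibration curve and 95% confidence band for each model. Correct it for optimism by bootstrap, or obtain it by applying one centre's model to the other centre's data, which the pooling in section 4.4 makes possible.
2. Report calibration intercept and slope with 95% confidence intervals from that corrected or cross-centre assessment, not from the fitting data.
3. Allow for non-linearity of each continuous biomarker in the updated model, by log transform or restricted cubic spline.
4. State that a non-significant goodness-of-fit test will not be taken as evidence of calibration.

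**Cost.** A change of wording and a little more analysis on data already being collected; no extra patients, samples or visits. There is no longer a single p-value to report. Splines use one or two extra degrees of freedom per biomarker, which matters if MACE events are as few as 18-36. Cross-centre intervals will be wide at such counts: with 18 events in a centre, observed/expected is known only to about 0.64-1.57. If Toronto data are not available, the bootstrap is the remaining option.

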1. INTRODUCTION AND RATIONALE

Worldwide, over 300 million patients undergo major noncardiac surgery every year¹ and this number has been increasing continuously². Despite the beneficial aspects of surgery, approximately 19% of these patients will suffer an in-hospital major adverse postoperative event (MAPE)³. The most common MAPE had an infectious (33%) or cardiovascular origin (19%) with highest mortality rates observed in patients with a major adverse cardiac event (7.0%)³. Major adverse cardiac events (MACE) are a leading cause of postoperative morbidity and mortality⁴⁻⁷ and is associated with prolonged hospitalization and increased medical costs⁸.

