function, in patients with PMI and thereby, patients will be treated more appropriately and major complications could (hopefully) be prevented.

Nowadays, the Revised Cardiac Risk index (RCRI) is commonly used as a predictive tool to estimate the probability of MACE or mortality¹³. The RCRI includes six predictors, which are high risk surgery, history of myocardial infarction (MI), history of cerebrovascular disease, chronic heart failure, elevated creatinine and insulin dependent diabetes. Ford et al. performed a review on the performance of the RCRI in several validation studies and found that this cardiac index only moderately predicts, does not predict events in vascular surgery, and has not been prospectively validated using troponin or other biomarkers to predict MI or other cardiac events¹⁴. Since this publication, several studies reported the added predictive value to the RCRI of one (or more) biomarker(s), including (high sensitive) troponin¹⁵⁻¹⁷, (NT-pro)BNP^{15,16,18-20}, eGFR^{21,22}, CRP^{18,20}, ECG^{23,24} and transthoracic echocardiography^{19,25}. Addition of (high sensitive) troponin, (NT-pro)BNP and/or CRP to the RCRI seems promising for the prediction of MACE as the predictive performance significantly improves compared to the RCRI by itself. To our knowledge, different combinations of several biomarkers together in addition to the RCRI have not been reported yet.

Our primary objective is to investigate and compare the independent prognostic effect of the different PMI phenotypes (myocardial infarction and NITE) and noncardiac MAPE on disability. We will be diagnosing the differing PMI phenotypes using clinical evaluation and biomarkers. The primary endpoint is disability. Disability is assessed using the World Health Organization Disability Assessment Score 2.0 (WHODAS 2.0)²⁶. Our primary hypothesis is that any postoperative troponin elevation regardless of its association with MACE or noncardiac MAPE is independently associated with an increased risk of death and disability.

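### Secondary objective 4 scores biomarker additions to the RCRI only on the data that fitted the models, so each model's c-statistic, and the gains for combinations with weak or many markers, will look too good

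*Combined protocol and SAP*

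**What the plan says.** Section 7.3, last bullet, states for secondary objective 4: "The added prognostic value of each of the biomarkers (or combinations of biomarkers) will be tested to predict MACE", in hospital and at 6 months, with biomarkers coded both continuously and by clinical thresholds. The models are logistic regressions on the six RCRI predictors plus biomarkers. On performance: "Discrimination and calibration of the prediction models will be assessed using the c-statistic, Hosmer-Lemeshow test". On the comparison with the traditional index: "The net reclassification index (NRI) and the Integrated Discrimination Index (IDI) will be calculated to quantify how well the updated RCRI reclassifies patients".

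The Summary (Study design) lists five blood markers: "high sensitive troponin, brain natriuretic protein, C-reactive protein, creatinine and hemoglobin". Section 5.1.3 adds ECG and echocardiography as imaging biomarkers. Section 1 presents combinations as the new element: "different combinations of several biomarkers together in addition to the RCRI have not been reported yet". It also says which markers it expects to work: "Addition of (high sensitive) troponin, (NT-pro)BNP and/or CRP to the RCRI seems promising for the prediction of MACE".

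Section 4.4 says of the Toronto patients: "we will combine the data resulting in a total study population of 1,000 patients".

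The document mentions no bootstrap, cross-validation, shrinkage, split sample or external validation set. Section 7.3 names no primary combination, selection rule or NRI type or cut-offs. It does not say whether the traditional RCRI is the sum score or the six predictors refitted, nor which test of added value is meant.

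**The concern.** A model scored on the patients who supplied its coefficients looks better than it will in new patients. The effect grows with the number of coefficients and shrinks with the number of events. Five markers on six RCRI predictors give 11 slopes. At 37 events that is 37/11 = 3.4 events per slope, and at 110 events it is 110/11 = 10.

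At stake is the new claim of objective 4: whether several biomarkers together improve on the RCRI or on a single biomarker. A combination padded with uninformative markers can appear to beat a single marker while predicting worse. If the reference is the sum score, the benefit of re-estimating six RCRI weights is also credited to the biomarkers.

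**Working it through.** **Plan's own figure.** There is none for objective 4. The sample size in section 4.4 serves the WHODAS comparison; only its total is used here (500 + 500 = 1,000).

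**Inputs from the document.** N = 1,000, six RCRI predictors and five blood markers. The MACE rate is not given, but can be bracketed:
- Section 1: 19% of patients have a MAPE and 19% of those are cardiovascular, so 0.19 × 0.19 = 3.6%.
- Summary and section 4.4: PMI in 11 to 15%, one third of it infarction, so infarction alone is 3.7 to 5%.
- Section 7.3 counts PMI and NITE within MACE, which would imply 11 to 15%.

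**Assumptions, set A** (1,000 runs per setting; 10,000 new patients per run): RCRI items with prevalence 30/12/10/6/6/5% and odds ratio 2 each; independent standard normal markers; useful markers with log odds ratio 0.5 and 0.25 per SD; MACE 3.7, 8 and 11%.

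**Assumptions, set B** (400 runs for prespecified models, fewer for searches; 15,000 new patients): RCRI odds ratios 1.6 to 2.0; markers correlated 0.25; 37 to 150 events.

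**Quantities.** Apparent gain = c(RCRI + markers) − c(RCRI), with both models fitted and scored on the same 1,000 patients. New-patient gain = the same fitted models scored on fresh patients. Overstatement = apparent − new-patient.

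**Gain in c over the refitted RCRI, set A, at MACE 3.7 / 8 / 11%:**

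| Markers added | Apparent | New patients | Overstatement |
|---|---|---|---|
| One useful (0.5) | 0.052 / 0.053 / 0.055 | 0.054 / 0.055 / 0.055 | −0.002 / −0.002 / 0.000 |
| One useless | 0.010 / 0.006 / 0.005 | −0.004 / −0.002 / −0.001 | 0.014 / 0.008 / 0.006 |
| Two useful + one useless | 0.070 / 0.069 / 0.069 | 0.059 / 0.062 / 0.062 | 0.011 / 0.007 / 0.007 |
| Two useful + three useless | 0.078 / 0.072 / 0.070 | 0.052 / 0.057 / 0.059 | 0.026 / 0.015 / 0.011 |
| Five useless | 0.034 / 0.021 / 0.017 | −0.015 / −0.010 / −0.007 | 0.049 / 0.031 / 0.024 |

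Further runs with independent markers gave +0.013 to +0.027 for five weak markers (0.25 each) and −0.005 to −0.001 for two strong ones (0.5 each).

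**Set B, gain in c.** Twelve terms, two useful: 0.108 apparent against 0.053 at 37 events; 0.092 against 0.065 at 110. Best pair chosen from twelve: 0.067 against 0.013; 0.051 against 0.029. Five correlated markers, all useful (odds ratio 1.3): overstated by only 0.002 to 0.004.

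**Model's own c, one useful marker (0.5).** About 0.73 apparent against 0.67 at 3.7%, and 0.71 against 0.69 at 11%. The gain is nearly right because the optimism from the six RCRI weights sits in both models and cancels.

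**Five markers against one** (one useful, four useless, 800 runs). Apparent difference in c +0.017 / +0.009 / +0.007, positive in 92 to 94% of studies; in new patients −0.015 / −0.008 / −0.006.

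**NRI and IDI.** Continuous NRI, two useful + three useless (set A): 0.53 / 0.48 / 0.47 apparent against 0.37 / 0.40 / 0.40. In set B at 37 events:
- Twelve terms: NRI 0.68 against 0.36, IDI 0.044 against 0.020.
- Two useful markers (odds ratio 1.5): IDI 0.026 against 0.020.
- One useful marker (odds ratio 1.8): IDI 0.020 against 0.017.

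**Sum score as comparator.** Refitting the six predictors raises apparent c by 0.027 / 0.016 / 0.013 before any biomarker enters. Set A gives all six the same odds ratio, so this is chance fitting. If the true weights differ in this cohort, part of it would be real, but still not biomarker value.

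**The case against.** - **Silence is not a decision against validation.** This is a short protocol and the last of four secondary objectives. That is fair, and it limits the weight of the point. But the section proposes an updated index and says how its improvement will be measured; followed literally, that yields apparent values.
- **A small set of good markers is reported about right.** This stands for the gain in c. A reader might infer that every combination's gain in c is inflated. The document does not support that: section 1 expects troponin, BNP and/or CRP to help, and for a few strong markers the gain shows no upward bias. Overstatement needs weak or useless markers, many terms or a search, none of which section 7.3 rules out.
- **3.7% is close to a floor.** This also stands. Infarction alone reaches 3.7 to 5%, and the composite is wider, so the 8 to 11% figures are the fairer guide.
- **Markers are not independent.** Troponin enters the infarction definition and creatinine is an RCRI item. In set B, correlation made the overstatement for five useful markers much smaller. The sizes cannot be read as predictions for this study.

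Two further readings go too far. One is that useless biomarkers would often be declared significant through NRI or IDI. Section 7.3 only says these will be calculated and names no test on them, so no false-positive rate of the plan follows. The other is that one useful prespecified biomarker is free of the problem. Only its gain in c is, and only against a refitted RCRI; the model's own c and its IDI remain optimistic.

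**Conclusion.** The point holds in this form, as a gap that should be closed before analysis:

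1. Each model's own c-statistic will be optimistic, even with one useful biomarker.
2. The gain in c over a refitted RCRI will be overstated when a combination contains weak or useless markers, has many terms or is found by search. The main illustration, two useful and three useless markers, gives 0.011 to 0.015 at 8 to 11% MACE and 0.026 at 3.7%. The gain is about unbiased for one useful prespecified marker or a few strong ones.
3. NRI and IDI are overstated more generally for combinations, and IDI somewhat even for one or two useful markers.
4. If the reference is the sum score, about 0.013 to 0.03 of the reported gain in c is refitting.

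The direction follows from the text of section 7.3. The sizes rest on assumed marker effects, mostly independent markers, and a MACE rate that the document leaves anywhere from about 3.6% to 11 to 15%. The primary WHODAS analysis is not touched.

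**What to change.** In the last bullet of section 7.3:

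1. Prespecify a small set of biomarker additions.
2. State that the comparator is the six RCRI predictors refitted in the same cohort.
3. Test added value by a nested likelihood-ratio test.
4. Bootstrap the whole model-building procedure, including any marker selection and the choice between continuous and threshold coding. Report the optimism-corrected c-statistic, change in c, and calibration slope and intercept. Dropping the Hosmer-Lemeshow test is optional.
5. Report NRI (type and any cut-offs stated) and IDI as descriptive measures, noting that the bootstrap corrects NRI only in part.

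Fitting at one centre and checking at the other would be a useful addition, not a substitute.

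The cost is a little programming and smaller reported gains for combinations; no new data are needed. The bootstrap removes most of the excess, not all. With two useful and three useless markers it brought the gain in c from 0.078 / 0.072 / 0.071 to 0.059 / 0.060 / 0.060, against new-patient values of 0.052 / 0.057 / 0.059. With five useless markers, continuous NRI fell from 0.30 / 0.21 / 0.17 only to 0.10 / 0.07 / 0.05. For one useful prespecified marker the correction barely changes the gain in c.

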2.2 Secondary objectives

1. To investigate and compare the independent prognostic effect of the different PMI phenotypes (myocardial infarction and NITE) and noncardiac MAPE on disability free survival in patients undergoing elective noncardiac surgery.
2. To examine whether (combinations of) perioperatively measured cardiac biomarkers are associated with in-hospital major adverse postoperative events (MAPE) in patients undergoing elective noncardiac surgery. MAPE are divided in different subtypes, including:
 - a. Major adverse cardiovascular events (MACE), which is defined as the composite endpoint of cardiovascular death, non-fatal myocardial infarction, non-fatal cardiac arrest, non-fatal ventricular fibrillation, ventricular hemodynamic compromise, atrial fibrillation requiring cardioversion, pulmonary embolism and stroke.
 - b. Noncardiac major adverse postoperative events (MAPE) including sepsis, renal failure, unexpected ICU admission and respiratory failure.
 - c. All-cause mortality
3. To examine whether (combinations of) perioperatively measured cardiac biomarkers are associated with 6-month MACE and all-cause mortality in patients undergoing elective noncardiac surgery.
4. To assess the added value of the perioperatively measured biomarkers on top of the currently used Revised Cardiac Risk Index (RCRI) to predict major adverse cardiac events (MACE) after noncardiac surgery.

[figure not shown]

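### The NRI and IDI in Section 7.3 compare a refitted RCRI-plus-biomarker model with an undefined traditional RCRI, so part of the gain credited to biomarkers can come from refitting

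*Combined protocol and SAP*

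**What the plan says.** Objective 4 (Section 2.2) asks what the perioperative biomarkers add to the RCRI as currently used for predicting MACE. Section 1 describes that index as "commonly used as a predictive tool to estimate the probability of MACE or mortality" and states that "The RCRI includes six predictors".

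The analysis is in the last item of Section 7.3:

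- **Updated model.** "Multivariable logistic regression analyses will be performed using the predictors of the RCRI", with the six items listed one by one "as predictors together with the addition of elevation in biomarkers". Each item therefore gets its own coefficient, estimated in the study data.
- **Model performance.** "Discrimination and calibration of the prediction models will be assessed using the c-statistic, Hosmer-Lemeshow test". Which models are meant is not stated.
- **Added value.** NRI and IDI are the measures named, and their stated purpose is to "quantify how well the updated RCRI reclassifies patients as compared to the traditional RCRI".

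The plan does not say whether the traditional RCRI is the point total, a set of published risks, or the six items refitted. It names no six-predictor model without biomarkers, and no likelihood-ratio test or optimism correction.

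**The concern.** On the plain reading, two things differ between the models being compared: the weights on the six RCRI items, and the presence of biomarkers. NRI and IDI cannot separate them. A biomarker with no predictive information could then appear to improve classification because the index was reweighted to this population and this MACE composite.

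The documents give reason to expect reweighting to matter. Section 1 reports only moderate performance of the RCRI, and failure in vascular surgery. The composite in Section 5.1.2 includes pulmonary embolism, stroke and atrial fibrillation needing cardioversion. NRI and IDI are the only between-model comparisons named, so they are the likely headline for objective 4.

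**Working it through.** The plan gives no expected NRI, IDI or MACE rate for this analysis, so there is no figure to reproduce. The check is algebra plus simulation.

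**Algebra.** Let D(M) be the mean predicted risk in patients with MACE minus the mean in those without, under model M. Let T be the traditional RCRI, S the six items refitted, and U the six items refitted plus biomarkers. Then

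IDI(U vs T) = D(U) − D(T) = [D(S) − D(T)] + [D(U) − D(S)].

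The first bracket is refitting alone; only the second concerns biomarkers. The c-statistic difference splits the same way. NRI does not split exactly but has the same two sources.

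**Inputs from the documents.** Six RCRI items (Section 1); five blood biomarkers (Section 5.1.3); N = 500 at one centre and 1,000 pooled (Section 4.4).

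**Assumed inputs.** MACE 4%, 7% or 10%; item prevalences 35, 10, 12, 6, 6 and 7%; true log odds ratios either all 0.7 (equal) or 1.2, 0.3, 0.6, 1.2, 0.9 and 0.1 (unequal). All five biomarkers are pure noise. T is the 0–6 point total with intercept and slope recalibrated in the same data, which favours T. There were 300 data sets per setting.

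Mean apparent gain at N = 1,000, shown as c-statistic / IDI:

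| True weights | MACE | S vs T (refitting) | U vs T (plain reading) | U vs S (biomarkers) |
|---|---|---|---|---|
| equal | 4% | 0.027 / 0.009 | 0.055 / 0.017 | 0.028 / 0.008 |
| equal | 7% | 0.018 / 0.008 | 0.039 / 0.015 | 0.021 / 0.007 |
| equal | 10% | 0.014 / 0.008 | 0.032 / 0.014 | 0.018 / 0.006 |
| unequal | 4% | 0.040 / 0.018 | 0.067 / 0.027 | 0.026 / 0.009 |
| unequal | 7% | 0.033 / 0.020 | 0.051 / 0.027 | 0.018 / 0.007 |
| unequal | 10% | 0.032 / 0.023 | 0.047 / 0.029 | 0.015 / 0.006 |

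The IDI columns add up as the algebra requires (for example 0.020 + 0.007 = 0.027). Refitting makes up between 0.009/0.017 = 53% and 0.023/0.029 = 79% of the apparent IDI. Refitting alone gives a continuous NRI of 0.18–0.28 (equal) or 0.52–0.56 (unequal). At N = 500, the IDI of U vs T is 0.027–0.050, of which refitting contributes 0.014–0.031.

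**One noise biomarker.** With n = 1,000, 6.4% MACE, assumed prevalences of 6–30% and recalibrated points, the apparent IDI against T is about 0.010 (equal weights) to 0.021 (unequal, log odds ratios 0.2–1.2). Against S it is about 0.0015.

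**How much is optimism.**
- At N = 100,000 and 7% MACE, where overfitting is negligible, the IDI of U vs T is 0.0001 with equal weights and 0.0121 with unequal weights. U vs S is 0.000 in both.
- With one noise biomarker and models fitted at n = 1,000 but evaluated in fresh data, equal weights give an IDI of about 0 and a c-statistic change of −0.013 against T. Unequal weights give an IDI of 0.009–0.012, about half the apparent value. Of the c-statistic gain, only about one seventh (0.006/0.044 = 0.14) to one quarter remains.

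**The biomarker coefficient.** In the planned six-item-plus-biomarker regression, the Wald test rejected a single noise biomarker in 4–6% of cohorts, close to the nominal 5%.

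**IDI z-test.** The plan does not name a test for the IDI. If z > 1.96 were used at N = 1,000, refitting alone would exceed it in 42–47% of data sets (equal) or 69–94% (unequal). Even U vs S with five noise biomarkers exceeds it in 33–42%, so this z-test should not decide added value against either reference.

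**The case against.** **The comparator may already be the right one.** The text lists the six predictors as regression terms and then adds biomarkers, so updated versus traditional could mean with versus without biomarkers in the same regression. IDI needs predicted probabilities, and the protocol contains no table from points to risk, so some fit or outside table is needed in any case. If the sponsor means the refitted predictors, the reweighting problem disappears. This stands as a limit: a reader might infer that a wrong comparator is proven, but the documents show an undefined one whose plain reading is the existing index. One clarifying sentence is needed either way.

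**Much of the gap is overfitting.** This also stands. A reader might infer that the whole gap is a comparator effect that would carry over to validation data. It would not: with equal true weights nothing carries over, and with unequal weights only part does. The documents do not say which case applies.

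**Added value is also tested within the model.** Section 7.3 says added prognostic value will be tested, and specifies a regression in which each biomarker is already adjusted for the refitted items. That coefficient is a valid conditional test, so it would be wrong to conclude that objective 4 has no sound analysis. The c-statistic is likewise not tied to the traditional RCRI in the text; a c-statistic contrast is affected only if made against that index.

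**Comparison with the tool in use is legitimate.** Agreed, as a description of the updated model as a whole. It does not isolate the biomarkers.

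**Conclusion.** The point holds for the NRI and IDI comparison, and for any c-statistic difference taken against the existing index. On the plain reading, these measures mix reweighting with biomarker value. A useless biomarker would show an apparent IDI of about 0.01–0.02 rather than about 0.0015 (n = 1,000, about 6.4% MACE, recalibrated points).

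The direction was the same in every setting at the planned sample sizes. The size rests on assumed MACE rates, prevalences and weights, none of which the documents give. The NRI is especially sensitive: its value in new data with unequal weights was 0.14 under one set of assumptions and 0.34 under another. A reader might also infer that refitting accounts for nearly all of any reported gain. The share depends on how many biomarkers enter and whether they carry information; with five noise biomarkers it was 53–79% of the IDI at N = 1,000.

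This affects one of four secondary objectives and not the primary analysis. It should be corrected before the analysis is run.

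**What to change.** In Section 7.3:

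1. Define the reference model for NRI, IDI and c-statistic difference as the six RCRI predictors refitted by logistic regression, without biomarkers, on the same patients and the same MACE definition as the updated model.
2. Base the test of added value on the nested comparison: the likelihood-ratio statistic 2[log L(U) − log L(S)] on as many degrees of freedom as there are biomarker terms, or the biomarker coefficient where a single term is added.
3. Define the traditional RCRI (points, published risks or other) and report it as a separate descriptive comparison, so that the link to current practice is kept.

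The cost is one sentence and one additional model fit, with no new data. Reported gains will be smaller. The change removes the reweighting component only. Optimism from the biomarker terms remains (IDI 0.006–0.009 with five noise biomarkers at N = 1,000), so correction for optimism is still a separate need.
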